8.3 Other Assessment Instruments

8.3.1 *Mini International Neuropsychiatric Interview, Version 7.0.2*

The MINI was designed as a brief structured interview for the major Axis I psychiatric disorders in DSM-5 and International Classification of Diseases-10. Validation and reliability studies have been done comparing the MINI to the Structured Clinical Interview for DMS-5 Patient Edition and the Composite International Diagnostic Interview (a structured interview developed by the World Health Organisation). Version 7.0.2 of the MINI will be used for this study. The results of these studies show that the MINI has similar reliability and validity properties, but can be administered in a much shorter period (mean 18.7 ± 11.6 min, median 15 min) than the above referenced instruments. It can be used by clinicians after a brief training session.²⁷

At screening, the presence of inclusionary and lack of exclusionary psychiatric diagnoses will be confirmed by use of the MINI 7.0.2.²⁷

8.3.2 *McLean Screening Instrument for Borderline Personality Disorder*

The MSI-BPD is a commonly used measure to assess for BPD. The scale consists of 10 items based on the DSM-5 BPD criteria; the first 8 items represent the first eight criteria in the DSM-5 for BPD diagnosis, while the last two questions assess the paranoia and dissociation criteria for BPD. Scores for the MSI-BPD range from 0 to 10, with each item rated as “1” if present and “0” if absent. A score of 7 or higher indicates a likelihood for the participant to meet criteria for BPD. The MSI-BPD will be collected at Screening only and participants positive for BPD will be subject to clinical confirmation of diagnosis by the study clinician and Medical Monitor.

8.3.3 *International Trauma Questionnaire*

The ITQ is a brief, self- reported questionnaire, focusing on the core features of PTSD and complex PTSD. The ITQ was developed to be consistent with the ICD-11 principles, as set for the World Health Organisation. It can be used to diagnose PTSD, if the participant endorses one of the two symptoms clusters of (1) re-experiencing in the here and now, (2) avoidance, and (3) sense of current threat, plus endorsement of at least one indicator of functional impairment associated with these symptoms. Complex PTSD required endorsement of one of the two symptoms from each of the three PTSD symptoms clusters and one of two symptoms

from each of the three Disturbances in Self-Organisation (DSO) clusters: (1) affective dysregulation, (2) negative self-concept, (3) disturbances in relationships. Functional impairment must be identified where at least one indicator of functional impairment is endorsed related to the PTSD symptoms and one indicator of functional impairment is endorsed related to the DSO symptoms.¹⁷

8.3.4 PTSD Checklist for DSM-5

The PCL-5 is a 20-item self-reported scale, used for provisional PTSD diagnosis, screening and symptoms monitoring purposes. The participant will complete the past month version of this assessment at screening, scoring the severity of their symptoms on a 5-points Likert scale where 0 = not at all and 4 = extremely.¹⁸ The screener should help the participant understand this scale and in its correct completion to ensure the PCL-5 is used to measure the relevant Criterion A for the trauma. The past day version of the assessment will be used at day 2. The past week version of the assessment will be administered at baseline and weeks 1, 2, 4, 6, 9, and 12.

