8.1 General

8.1.1 *Change from Baseline*

Table 4: Change from Baseline Definition

Definition	Derivation
Change from baseline	= post-baseline visit value - baseline value

If there is no baseline or post-dose visit value, then the absolute and change from baseline will be set to missing.

8.1.2 *Missing and Partial Dates*

All rules explained in Section 8.2.10 for partial / missing dates will be followed unless contradicted by any other data recorded on the electronic Case Report Form (eCRF).

All dates presented in the individual participant listings will be as recorded on the eCRF. In case of partial eCRF entries, the rules described in Sections 8.2.10.1 will be used for date imputation for the purposes of deriving ancillary quantities (e.g. study day, duration of an event, etc) but only partial dates will be presented in the listings.

8.1.3 *Treatment Exposure and Compliance*

Since the frequency of administration of COMP360 is only once, calculations of treatment exposure and compliance are not applicable.

8.1.4 *Inexact Values*

In the case where a variable is recorded as “> x”, “ \geq x”, “ $< x$ ” or “ $\leq x$ ”, the value of x will be taken for analysis purposes. This rule will be applied to continuous laboratory parameter values only for summary tables and figures, whereas listings will show the actual value recorded (inclusive of the non-numeric symbol).

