A total symptom severity score (range 0-80) can be obtained by summing the scores for each of the 20 items. The symptom cluster severity score can be obtained by summing the scores for the items within a cluster, as defined in Table 11.

Table 11: PCL-5 Item Mapping to Cluster

Criterion	Symptom Number
B	1, 2, 3, 4, 5
C	6, 7
D	8, 9, 10, 11, 12, 13, 14
E	15, 16, 17, 18, 19, 20

The PCL-5 ‘Screening’ version will be used at Screening (Visit 1). The ‘past day’ version will be used at Day 2 (Visit 2) and the ‘past week’ version of the assessment will be used at Baseline and at Weeks 1, 2, 4, 6, 9, and 12 (Visits 3, 5, 6, 7, 8, 9, and 10, respectively).

8.4.3 *Sheehan Disability Scale (SDS)*

The SDS is a brief, five-item self-report inventory assesses functional impairment in work/school (score ranges from 0 to 10), social life (score ranges from 0 to 10), and family

life (score ranges from 0 to 10).¹¹ The sum of the above three domain scores lead to a SDS total score ranging from 0 to 30 with 0 representing no impairment and 30 representing severe impairment. The past week version of the SDS will be performed.

For the main derivation, if the participant selects ‘I have not worked/studied at all during the past week for reasons unrelated to the disorder’, and has not answered the work/school item, the total score will be prorated by multiplying the scores of questions 2 (social life) and 3 (family life) by 1.5.

In addition to the main derivation, a sensitivity derivation will be calculated as follow: if a participant ticks the ‘I have not worked/studied at all during the past week for reasons unrelated to the disorder’ box and has not answered the work/school item, then no SDS total score will be derived.

The SDS data will be obtained at Baseline, Week 4, and Week 12 (Visits 2, 7, and 10, respectively).

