11.1 Secondary Efficacy Endpoint(s)

The secondary endpoints are:

- Change in CAPS-5 total symptom severity score and criteria scores from baseline
- Change in PCL-5 total symptom severity score and cluster severity scores from baseline
- Change in SDS total score from baseline
- Change in EQ-5D-5L index score from baseline
- Proportion of participants with response (defined as a ≥ 15 point improvement on the CAPS-5 total score from baseline)
- Proportion of participants with remission (defined as CAPS-5 total score ≤ 20)

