11.1.1 Main Analysis

Total/total severity/index score values and their changes from baseline at each post-baseline timepoint will be descriptively summarised using statistics for continuous variables including 95% CIs for the FAS. Both actual values and their change from baseline will also be graphically displayed as line plots for the FAS. All observed scale data will also be listed. These summaries, figures and listings will be presented for the scales below:

- CAPS-5 (*Table 14.2.2.1*, *Figure 14.2.2.1*, *Listing 16.2.6.1*)
- PCL-5 (*Table 14.2.2.2*, *Figure 14.2.2.2*, *Listing 16.2.6.2*)
- SDS (*Table 14.2.2.3*, *Figure 14.2.2.3*, *Listing 16.2.6.3*)
- EQ-5D-5L (*Table 14.2.2.4*, *Figure 14.2.2.4*, *Listing 16.2.6.4*)

The proportion of CAPS-5 responders (defined as a ≥ 15 point improvement on the CAPS-5 total score from Baseline) and CAPS-5 remitters (defined as CAPS-5 total score ≤ 20), will be descriptively summarised alongside 95% asymptotic CIs at each post-baseline timepoint (*Table 14.2.2.5* for response and *Table 14.2.2.6* for remission) and graphically

displayed via bar charts including the estimated 95% Wald-type CIs (*Figure 14.2.2.5* for response and *Figure 14.2.2.6* for remission). At each timepoint separate proportions will be calculated using both the total number of participants in the FAS (N) and the total number of participants with available data at a particular visit as the denominator (n*).

CIs will be Wald-type asymptotic intervals based on the Normal approximation to the binomial distribution, obtained in SAS as follows:

```
ods output BinomialCLs = <output-dataset>;
proc freq data = ;
  by avisitn;
  tables aval / binomial (level = 2 cl = wald);
run;
```

Participant's status as a responder/remitter at each timepoint will be listed (*Listing 16.2.6.1*).

Participant's status as a remitter at each timepoint will be listed (*Listing 16.2.6.1*).

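### The Day 2 PCL-5 change from baseline subtracts a past-week score from a past-day score, so it is not comparable with the changes from Week 1 onward

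*Protocol*

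**What the plan says.** **Which form is used when.** Protocol 8.3.4 uses three recall windows for the PCL-5:

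- Screening: "The participant will complete the past month version of this assessment at screening".
- Baseline and follow-up weeks: "The past week version of the assessment will be administered at baseline and weeks 1, 2, 4, 6, 9, and 12".
- The day after dosing: "The past day version of the assessment will be used at day 2".

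SAP 8.4.2 makes the same split between Day 2 and the other visits. The past-day "version will be used at Day 2 (Visit 2) and the" past-week "version of the assessment will be used at Baseline and at Weeks 1, 2, 4, 6, 9, and 12".

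**How it is analysed.** SAP 11.1 lists as a secondary endpoint "Change in PCL-5 total symptom severity score and cluster severity scores from baseline". Table 4 in SAP 8.1.1 defines change as "post-baseline visit value - baseline value", with no rule about form or recall window. SAP Table 17 sets the efficacy baseline at Day -1. SAP 11.1.1 then provides that scores and "their changes from baseline at each post-baseline timepoint will be descriptively summarised", with 95% CIs, and that observed values and changes are both drawn as line plots. For the PCL-5 these are Table 14.2.2.2 and Figure 14.2.2.2.

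The schedules in both documents include the PCL-5 at Day 2.

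**The concern.** Day 2 is the first PCL-5 after dosing, so it is where a reader looks for early onset. The SAP treats it as the first point of a series measured in one way, but it is the only post-baseline visit with a different recall window from baseline.

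The window is also unusual in content. Under Protocol 5.1 and 9.3 the preceding day is the administration day: a session of about 6 to 8 hours, in a dimly lit room with two therapists present, under acute drug effects. A participant describing that day is describing something different from the ordinary week described at baseline.

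At stake is the meaning of one estimate, its interval and one plotted point of a secondary endpoint. The trial is open label with one arm, so no comparison group would share and cancel the shift. A 95% CI reflects sampling variation only and cannot show it.

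**Working it through.** The documents give no figure to reproduce: no hypothesis, power calculation, assumed SD or expected PCL-5 change. The check is a trace of the derivation, followed by an illustration on assumed values.

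**1. Trace.** Write W for a past-week score and D for a past-day score.

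| Visit | Form | Change computed under SAP 8.1.1 and Table 17 |
|---|---|---|
| Day -1 | W | baseline |
| Day 2 | D | D(Day 2) − W(Day -1) |
| Weeks 1, 2, 4, 6, 9, 12 | W | W(week) − W(Day -1) |

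One of seven post-baseline visits is mismatched.

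**2. What the Day 2 difference contains.** Adding and subtracting a past-day score at Day -1 gives

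D(Day 2) − W(Day -1) = [D(Day 2) − D(Day -1)] + [D(Day -1) − W(Day -1)].

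The second bracket is a pure recall-window difference that exists without any drug. The first holds any treatment effect together with the effect of having spent the day in a dosing session. D(Day -1) is not collected, so the plan cannot estimate the brackets separately.

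**3. Search for a safeguard.** SAP 8.1.1, 8.4.2 and 11.1.1 do not exclude, separate or footnote Day 2. SAP Section 12 (changes from the protocol) lists only the FAS definition and the AESI terms. The post-lock addendum adds or revises several outputs, none of them on this point.

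**4. Possible size (assumed values).** The total is the sum of 20 items scored 0 to 4, with a range of 0 to 80. If window and setting shift m items by one point each in the same direction, the total shifts by m points:

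| Items shifted | Shift in total |
|---|---|
| 0 | 0 |
| 3 | ±3 |
| 5 | ±5 |
| 10 | ±10 |

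For scale, take n = 20 (SAP 4.6 expects about 20) and a t-based 95% CI with half-width t(0.975; 19) × SD/√20, where t = 2.093:

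- SD of change 10: 2.093 × 10/4.472 = 4.7 points
- SD of change 15: 7.0 points
- SD of change 20: 9.4 points

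Under these assumptions a 5-point shift is about as large as the half-width at SD 10, and about half of it at SD 20 (5/9.4 = 0.53). It could be visible in the plot, and the interval would not account for it.

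**The case against.** **The past-day form is a reasonable choice at Day 2.** A past-week form completed the day after dosing would cover mostly pre-dose days. This stands. The fault is differencing the past-day score against a past-week baseline without separation or caveat.

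**Little depends on this value.** No hypothesis is tested, SAP Section 11 calls the intervals exploratory, the primary objective is safety, and response and remission use CAPS-5, which has the last-month form at baseline and at Weeks 4 and 12. This also stands and limits the weight of the point. A descriptive result must still describe one quantity.

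**A reader might infer that the plan will show a spurious improvement right after dosing**, because a shorter window gives intermittent symptoms less chance to appear. For example, if symptom days fall at random, a symptom present on 2 of 7 days is absent from a given day with probability 1 − 2/7 = 0.71. The documents do not support that inference. The 0.71 is a chance of absence, whereas PCL-5 items rate severity, so it does not convert into points. The window also covers the dosing session, for which Protocol 1.2.2 expects perceptual and mood changes and Protocol 11.9 lists dissociation, disturbed attention and altered mood as events of special interest. Such experiences could raise item scores, so the net direction is unknown.

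**Removing a prespecified value after database lock is itself a post hoc change.** This is fair, and the fix below includes an option that keeps the value.

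**Conclusion.** The point holds as a matter of comparability. Followed as written, the plan reports a Day 2 PCL-5 change, a 95% CI and a plotted point that combine recall window and dosing-session setting with any treatment effect. The same applies to the PCL-5 cluster scores wherever their Day 2 change is reported. Neither the direction nor the size of the shift can be obtained from the documents; the point values above are illustrations only.

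The scope is one visit of one descriptive secondary endpoint. It would be wrong to read this as undermining the PCL-5 endpoint as a whole, because from Week 1 onward like is compared with like. CAPS-5 is unaffected.

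This rests on the Day -1 past-week form serving as baseline, as SAP Table 17 states. The general rule in SAP Section 7 takes the last value before dosing. If a Day -1 PCL-5 were missing, that rule could bring in the past-month screening score, so Table 17 should be taken to govern.

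The visit numbers in SAP 8.4.2 (Day 2 as Visit 2, Baseline as Visit 3) disagree with SAP Table 15. This is a clerical slip. A reader might take it as a sign that the wrong form was used at some visit, but both documents assign the forms by named day and week, and those assignments agree.

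**What to change.** In SAP 11.1.1, Table 14.2.2.2 and Figure 14.2.2.2:

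- Report the Day 2 past-day score as an observed value labelled with its recall window.
- Keep it out of the past-week change-from-baseline summary and out of the connected lines for both observed values and changes.
- If the Day 2 change is retained because it was prespecified, show it as a separate, unconnected point and table row, footnoted as a past-day score minus a past-week baseline and not comparable with later visits.

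Separately, align the visit numbers in SAP 8.4.2 with Table 15 (Baseline = Visit 2, Day 2 = Visit 4).

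No new data are needed. The cost is an edit to the SAP text, one table and one figure, with one early change value lost or caveated. The SAP has already been amended after database lock by addendum, and the same route would serve. The reason for the change should be given as the recall window, which was fixed in the protocol and does not depend on the results.

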8.3.5 Life Event Checklist for DSM-5

LEC-5 is a self-report measure designed to screen for potentially traumatic events in a respondent's lifetime. The LEC-5 assesses exposure to 16 events known to potentially result in PTSD or distress and includes one additional item assessing any other extraordinarily stressful event not captured in the first 16 items. For each item in the list the participant has the option to reply, "happened to me", "witnessed it", "learned about it", "part of my job", "not sure", "doesn't apply". The LEC-5 will be administered at screening together with the PCL-5.¹⁹

8.3.6 Childhood Trauma Questionnaire

The CTQ is a 28-item self-report measure validated to screen for history of childhood abuse and the meaning given to the abuse by the participant. It consists of 5 subscales measuring, physical abuse, sexual abuse, emotional abuse, physical neglect, and emotional neglect. The CTQ will be used at screening to exclude participants with childhood trauma.²⁰

8.3.7 Semi-structured PTSD management interview

Participants will be asked at baseline about their PTSD symptoms and feelings at the time of diagnosis and the type of treatments and support offered to them before joining the study.

8.3.8 Semi-structured qualitative interview

Participants will be asked their overall opinion of their experience with COMP360 therapy, if they consider a single dose enough, the impact of the experience on their lives and any feedback on the study design. This will occur at day 2 and week 12.

8.3.9 Measure Health app

If the participant opts to participate in the Measure Health portion of the study, the app will be activated on the participant's mobile phone at the screening visit; it will be deactivated at the

EOS. Participants who do not consent to the app installation, or do not have a smart phone, will not be excluded from the study.

Mobile data collection: The Measure Health app will collect data from the participant's smart phone and periodically send these data back to the HealthRhythms secure database. The participant will not need to do anything to collect these, except use their phone as they normally do. The data collected from the participant's phone will include:

- Activity data based on CoreMotion on iOS and the Activity Transition API on Android.
- Location information from the Location API on both iOS and Android, which uses GPS and/or cell tower location information.
- Device display status from Springboard on iOS and display on/off broadcast events on Android. These data are used to approximate when a user is actively using their phone.
- Pedometer data ("steps") based on CoreMotion on iOS and Google Fit on Android. The app may also maintain a list of target words and the participant's use-frequency of these words. These words will be completely stripped from their context, thus preventing the content of any particular message from being deciphered.

No personally identifiable information is captured, and all captured data are encrypted on the smartphone before upload to Measure Health cloud storage servers, and the data remain encrypted in transit and at rest.

8.3.10 Biomarkers measurements

If the participant opts to participate in this portion of the study, additional blood samples will be drawn. Participants who do not consent to blood withdrawal for biomarkers will not be excluded from the study, and clinical laboratory tests will still be run for safety purposes.

Blood samples to measure biomarkers levels will be collected at baseline, week 4, and week 12 after COMP360 administration. Up to 100mL of blood will be collected at each time point: total of ten 5 X 10ml EDTA tubes, one X 8.5ml serum tube, two X 2.5ml RNA PAXGene tube, and two X 8.5ml DNA PAXGene tube will be collected.

In addition to clinical laboratory measurements, the biomarkers measured will include biomarkers related to stress and inflammation such as plasma or serum cortisol, oxytocin, ACTH, catecholamines, BDNF, NPY, and cytokines; telomere length and telomerase activity; and the expression levels of stress-relevant mRNAs through transcriptomics and candidate gene analyses.

In addition, aliquots of the samples will be bio-banked for future studies, such as for genome-wide methylation, genome-wide expression, genotyping/GWAS (psych chip).

8.3.11 Magnetic Resonance Imaging

If the participant opts to participate in this portion of the study, brain imaging via MRI will be performed at baseline and week 4. The activity of brain regions will be monitored during the performance of a trauma narrative task and an emotional go/no-go task. Participants who do not consent to the MRI scan will not be excluded from the study.

8.4 Protocol Deviations

All protocol deviations will be assessed and documented on a case-by-case basis before the database lock.

9 INVESTIGATIONAL PRODUCT MANAGEMENT

9.1 Description

Information about the IMP is provided in Table 9.1.

Table 9.1 Details of Investigational Medicinal Product (IMP)

COMP360	
Ingredient	Synthetic psilocybin
Manufacturer	[REDACTED] [REDACTED] [REDACTED]
Dose	25 mg
Route	Oral
Formulation	Capsule
Strength	5 mg

9.1.1 Formulation

COMP360 5 mg capsules are manufactured by Catalent Pharma Solutions, Nottingham, UK.

9.1.2 Storage

All IMP must be kept in a locked area with limited access. The high-density polyethylene (HDPE) bottles of IMP are to be stored as indicated in the IMP Handling Manual. Deviations of storage temperature outside this required range should be documented and COMPASS or its designee should be notified promptly. Bottles of IMP should not be frozen. If any component of the IMP is damaged, COMPASS or its designee must be notified as soon as possible.

9.2 Packaging

COMP360 capsules are packaged into HDPE containers with child-resistant, tamper-evident screw cap lids with a mounted desiccant by [REDACTED]

[REDACTED] Each bottle contains 5 capsules for a single dose administration. Labels are affixed on to the bottles consistent with regulations in participating countries. Single individual bottles will be provided for use by a given participant.

9.3 Dose and Administration

Each participant will be assigned 1 treatment bottle containing the following:

- 5 x 5mg COMP360 capsules

After a light breakfast taken at least 2 h prior to IMP administration and under observation of study staff, the 5-capsule dose is to be swallowed with a full glass of water; due to the number

of capsules in a dose, additional water may be necessary to swallow the dose. Study staff will ensure the entire 5-capsule dose has been swallowed.

To prepare for the drug experience, the participant will take the IMP and lie down in a room with dim lights and a standard playlist of relaxing music playing quietly. Two trained therapists will be present with the participant at all times.

The effects of COMP360 usually start about 20 to 30 min after administration, become most intense in the first 90 to 120 min, and gradually subside after 5 to 6 h. The participants will be asked to remain in the room for the duration of the session regardless of the intensity of the effects, preferably lying down. A light meal and fruit will be available for the participant.

About 5 to 6 h after dosing, a trained therapist will discuss the study drug administration experience with the participant. The participant is to be discharged 6 to 8 h post-dosing when, in the opinion of the investigator, the acute effects of COMP360 are resolved. The participant will be accompanied home. The site is to be notified that they have returned home safely, and in the absence of receiving a phone call, site staff will directly contact the participant.

More details on preparation, administration, and integration sessions are available in the Therapist Manual.

